4. STUDY OBJECTIVES

The objectives of this study is to demonstrate the equivalency of efficacy and safety in reducing musculoskeletal pain between Piroxicam plus Counterirritant gel versus Piroxicam gel and Diclofenac gel, applied for 6 ± 1 days in Indonesian population.

Justification:

Piroxicam plus Counterirritant, Piroxicam, Diclofenac are considered as topical Non-Steroid Anti Inflammatory Drugs (NSAIDs). Diclofenac more common to use as a standard topical treatment since they have more clinical studies data than others topical NSAIDs. To demonstrate that Piroxicam plus Counterirritant has the same efficacy with Piroxicam, Diclofenac, the dedicated clinical study need to be conducted.

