5. STUDY DESIGN

This is a Phase 3, Randomized Control Trial, Multi centre, Single-blind, and Parallel group of 6 ± 1 days duration of data collection after topical application to compare the efficacy and safety of standard treatment of musculoskeletal pain in adult populations.

Justification :

- Phase 3 (Confirmatory study)
The study is conducted to demonstrate whether or not a product offers a treatment benefit to adult participants with musculoskeletal pain between test drug (Piroxicam plus Counterirritant) and commonly used NSAID topical products, Piroxicam gel, Diclofenac gel
- Randomized Control Trial (RCT)
Participants are randomly assigned to different treatment or control groups to minimize bias and allow for causal inference.
- Multi centre
The study will be conducted in 2 sites
- Single-blind
To keep this study maintain the integrity of the data, the investigational product will be given a white sticker to cover all over the tube of investigational products. On top of the tube, there is a study label with unique code to differentiate the test drug and comparator drug. With this procedure, participants will not know which products that assigned to them. Therefore participants can be blinded.
- Parallel

The study in which two groups of participants receive Piroxicam plus Counterirritant gel or Piroxicam gel, or Diclofenac gel. Participants are assigned to one of the treatment arms at the beginning of the trial and continue in that arm throughout the length of the trial. Assignment to a group usually is randomized.

5.1 Primary End-Point:

The primary end-point is the difference of musculoskeletal pain reduction ≥ 3 scores, of the response to treatment that can be seen through Brief Pain Inventory (BPI) scores.

Justification:

- The Brief Pain Inventory (BPI) scores.

It is a medical questionnaire that is used to assess pain. It has also been validated for pain assessment chronicle. There are 9 questions related to the pain experienced by the participants. The pain assessment will be given in the form of a score, namely a score of 0 - 10.

Score 0 : No Pain

Score 1 – 3 : Mild Pain

Score 4 – 6 : Moderate Pain

Score 7 – 10 : Severe Pain

The difference BPI scale ≥ 3 , from initial scale of pain to the end of treatment will be captured as the primary efficacy endpoint.

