7.9.1 Primary Endpoint

The assessment of primary endpoint will be assessed through form 2, Inventerisasi Rasa Nyeri Singkat on 1st Visit, 2nd Visit and 3rd Visit.

The primary end-point is the difference BPI scale ≥ 3 , from initial scale of pain to the end of treatment will be captured as the primary efficacy endpoint.

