7.4.2 Statistical Analysis Plan

The statistical analysis will be performed after data finalization and database lock, following the predefined analysis sets (PPS, FAS, and Safety Analysis Set). All analyses will be conducted using standard statistical software (e.g., SPSS, SAS, or R), with the level of statistical significance set at $p < 0.05$, unless otherwise adjusted.

Efficacy Analysis

- **Primary Endpoint (Pain Score using Brief Pain Inventory):**
 - **Test: Analysis of Covariance (ANCOVA)** adjusting for baseline BPI score

- **Equivalence testing:** Pairwise comparisons using **two one-sided t-tests (TOST)** to assess whether the difference in mean change from baseline falls within the equivalence margin (± 1.0)
- **Assumptions:** Normality and homogeneity of variance will be checked. If violated, non-parametric equivalent (e.g., **Wilcoxon rank-sum test**) will be used.
- **Secondary Endpoints:**
 - **Range of Motion (ROM) and Muscle Strength:**
 - **Test:** Repeated Measures ANOVA or mixed-effects model, depending on data completeness and correlation structure
 - If non-normal: **Friedman test** or **Wilcoxon signed-rank test** for within-group, **Kruskal-Wallis test** for between-group comparisons.
 - **Thermal Sensation, Comfort, and Acceptance (ASHRAE Scale):**
 - **Test:** Chi-square test or Fisher's exact test for categorical comparisons
 - **Ordinal regression** may be used to explore patterns of thermal perception across groups.
 - **Responding Analysis (pain reduction ≥ 3 points):**
 - **Test:** Chi-square test for group-wise comparison of response rates
 - **Risk difference** and **number needed to treat (NNT)** will be calculated.

Safety Analysis

- **Adverse Events (AEs) and Adverse Drug Reactions (ADRs):**
 - **Test:** Chi-square test or Fisher's exact test for comparing incidence across groups
 - Descriptive statistics for type, severity, onset, and duration
 - **Severity grading** and **causality assessment** using **Naranjo's algorithm**.
- **Rescue Medication Use:**
 - **Test:** Poisson regression or negative binomial regression if data are overdispersed
 - Summarized as a mean number of doses used per participant and compared between groups.

Demographic and Baseline Characteristics

- **Continuous Variables** (e.g., age, BMI):
 - **Test:** One-way ANOVA or **Kruskal-Wallis test** (if non-normal distribution)
- **Categorical Variables** (e.g., sex, diagnosis):
 - **Test:** Chi-square test or Fisher's exact test as appropriate

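### The ≥3-point response is named the primary endpoint of an equivalence trial, yet its only inferential test is a chi-square for difference with no margin or interval, which cannot support equivalent response

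*Protocol*

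**What the plan says.** Protocol section 4 states the aim: to "demonstrate the equivalency of efficacy and safety in reducing musculoskeletal pain" between the test gel and two active comparators.

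Two sections tie the primary endpoint to a fall of at least 3 BPI points. Section 5.1: "The primary end-point is the difference of musculoskeletal pain reduction ≥ 3 scores". Section 7.9.1 repeats the threshold and says that this difference, "from initial scale of pain to the end of treatment will be captured as the primary efficacy endpoint". The justification in section 5.1 treats such a fall as the sign that treatment works.

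Section 7.4.2 is organised differently. Its primary analysis is the BPI score by ANCOVA, with pairwise two one-sided tests (TOST) to "assess whether the difference in mean change from baseline falls within the equivalence margin" of ±1.0. The ≥3-point response stands under the secondary endpoints, with two lines: "Chi-square test for group-wise comparison of response rates" and "Risk difference and number needed to treat (NNT) will be calculated". No margin, confidence interval or decision rule is given for response. The general level is stated as "with the level of statistical significance set at $p < 0.05$, unless otherwise adjusted".

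**The concern.** The null hypothesis of a chi-square test is that the rates are equal. A small p-value would contradict equivalence. A large one says only that a difference was not detected, which in arms of this size is weak information. Neither result demonstrates equivalent response. The ±1.0 margin cannot be borrowed, because it is in BPI points and applies to a difference in means.

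This is not detail left for a later plan. The protocol names a test, and the test is of the wrong type for its objective. The same section uses TOST for the mean change, so it recognises that equivalence needs a margin.

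The importance depends on which section governs. If sections 5.1 and 7.9.1 do, the primary endpoint of an equivalence trial has no equivalence test at all. If section 7.4.2 does, the gap concerns a secondary result, though one that the protocol itself treats as the mark of effective treatment.

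**Working it through.** **Inputs from the protocol.** Section 6.7: 54 evaluable and 60 randomised per arm, SD 1.81, margin 1.0, alpha 0.05 or 0.05/3 = 0.0167. There is no response rate, response margin or response power to reproduce. The 54 is used as printed; it does not follow from its own inputs (2.39 + 0.84 = 3.23, not 4.059, and (3.23 × 1.81)² = 34.2), but that is a separate matter.

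**Assumptions.** True response is p₁ on the comparator and p₂ = p₁ − 0.20 on the test gel. The test is a pairwise Pearson chi-square without continuity correction, two-sided.

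**Step 1: chance of missing a 20-point deficit.** With p̄ the mean of the two rates, the approximation is

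miss = 1 − Φ{[0.20 − z·√(2p̄(1−p̄)/n)] / √[(p₁(1−p₁) + p₂(1−p₂))/n]}.

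For 70% versus 50%, n = 54, z = 1.96: √(2 × 0.6 × 0.4/54) = 0.0943, and √[(0.21 + 0.25)/54] = 0.0923. Then (0.20 − 0.1848)/0.0923 = 0.165, so miss = 1 − Φ(0.165) = 0.435. Exact enumeration of both binomials gives 0.434. The exact results are:

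| True rates | n = 54, 0.05 | n = 60, 0.05 | n = 54, 0.0167 | n = 60, 0.0167 |
|---|---|---|---|---|
| 60 v 40 | 0.47 | 0.39 | 0.63 | 0.60 |
| 70 v 50 | 0.43 | 0.38 | 0.62 | 0.55 |
| 80 v 60 | 0.37 | 0.32 | 0.55 | 0.50 |
| 90 v 70 | 0.24 | 0.20 | 0.41 | 0.34 |

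**Step 2: what a non-significant result can hide.** Take 38/54 against 29/54 responders. The difference is 0.704 − 0.537 = 0.167. With pooled rate 67/108 = 0.620, z = 0.167/0.0934 = 1.78 and p = 0.07. The unpooled standard error is 0.092, so the 95% interval is 0.167 ± 0.180, or −1 to +35 points. The test reports no significant difference while a 35-point deficit is not excluded.

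**Step 3: precision of the risk difference when rates are equal.** Half-width = z·√(2p(1−p)/n). At 95% and n = 54 this is 18.9, 18.5, 17.3 and 15.1 points for p = 0.5, 0.6, 0.7 and 0.8. At n = 60 it is 17.9, 17.5, 16.4 and 14.3. A 90% interval (one-sided 0.05) at n = 54 gives 13–16 points over the same rates. A level matching one-sided 0.0167 (z = 2.128) gives 16–20.

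**Step 4: is 20 points relevant on the protocol's scale?** If change is normal with SD 1.81, a 1.0-point shift in mean changes the response rate by Φ((m−3)/1.81) − Φ((m−4)/1.81), where m is the comparator's mean fall. For m = 2, 2.5, 3 and 3.5 this is 0.156, 0.188, 0.210 and 0.218. A 20-point deficit therefore lies near the protocol's own margin. Section 6.7 describes 1.81 as an SD of pain scores; using it for change is an assumption.

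**The case against.** The strongest reply is that section 7.4.2 rests the equivalence claim on the TOST for mean change, not on the chi-square. A reader might infer from the plan that a non-significant chi-square will be reported as equal response, or that the 32–47% is the trial's chance of a false equivalence conclusion. The protocol supports neither reading. It states no such rule for the chi-square.

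Under the Step 4 assumptions, the TOST would catch most such deficits. A 20-point response deficit corresponds to a mean difference of 1.81 × [Φ⁻¹(p₁) − Φ⁻¹(p₂)], which is 0.92 (60 v 40), 0.95 (70 v 50) and 1.07 (80 v 60). With standard error 1.81·√(2/54) = 0.348, TOST at one-sided 0.05 needs an estimate below 1 − 1.645 × 0.348 = 0.427. For 60 v 40 the chance is Φ((0.427 − 0.917)/0.348) = 0.08; for 80 v 60 it is 0.03. At one-sided 0.0167 it is at most 0.03. This stands, but only if mean change is the primary analysis, and sections 5.1 and 7.9.1 point elsewhere.

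It would also be too strong to say that response is compared by the chi-square alone, since a risk difference is planned. An interval around it could be left to a separate analysis plan. That answers the missing interval but not the choice of a difference test.

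The miss rates also depend on assumed response rates and alpha, as the table shows. Finally, removing the NNT is largely preference: nothing in the plan draws a conclusion from it.

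**Conclusion.** The point holds in a limited form. The only inferential test of the ≥3-point response tests for difference, has no margin or interval, and cannot support equivalence on that endpoint. It matters most if sections 5.1 and 7.9.1 define the primary endpoint, and less if section 7.4.2 does.

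With comparator response of 60–80%, two-sided alpha 0.05 and 54–60 per arm, a true 20-point deficit is missed in about 32–47% of trials. The figure falls to about 20–24% for 90% versus 70%, and rises to about 50–63% at alpha 0.0167 for the mid-range pairs. All of these rest on assumed rates, and they describe this test rather than the trial's overall equivalence claim.

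The matter should be corrected before database lock. It does not by itself invalidate an equivalence conclusion drawn from the mean-change TOST.

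**What to change.** 1. Reconcile sections 5.1 and 7.9.1 with section 7.4.2 on which endpoint is primary: mean BPI change or the ≥3-point response.
2. Base inference on response on the pairwise risk difference, test gel minus each comparator, with a confidence interval at the level used for the primary TOST. State that level, since section 6.7 adjusts alpha to 0.0167 and section 7.4.2 gives 0.05 "unless otherwise adjusted".
3. Add wording such as: A non-significant chi-square will not be taken as evidence of equal response. Similarity of response will be claimed only if the interval lies wholly within a margin fixed before database lock; otherwise response is descriptive.
4. The NNT may be dropped. If kept, it should not be used for inference, because 1/(risk difference) is unstable when the difference is near 0.

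This costs wording only, as the risk difference is already planned. The downside is precision: at 54 per arm and response of 50–70%, the 95% half-width is about 17–19 points, so similarity will often be out of reach. For illustration, TOST with a ±20-point margin at one-sided 0.05 and 80% power needs 2p(1−p)(1.645 + 1.282)²/0.20² per arm: about 108 at p = 0.5 and 69 at p = 0.8. If the ≥3-point response is confirmed as primary, the sample size must therefore be revisited. If mean change is primary, reporting response as descriptive is enough.

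### The ≥3-point BPI response is compared by an unadjusted chi-square test although baseline BPI is at hand; adjusting for it is a free gain in precision

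*Protocol*

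**What the plan says.** Protocol 5.1 states: "The primary end-point is the difference of musculoskeletal pain reduction ≥ 3 scores". It adds that the difference "from initial scale of pain to the end of treatment will be captured as the primary efficacy endpoint", and 7.9.1 repeats this. Section 7.9.1 also says that the endpoint "will be assessed through form 2, Inventerisasi Rasa Nyeri Singkat on 1st Visit, 2nd Visit and 3rd Visit", so every participant has a baseline BPI.

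Section 7.4.2 ranks the endpoints differently. Its primary analysis is the BPI score, by ANCOVA "adjusting for baseline BPI score" together with pairwise TOST at ±1.0. The ≥3-point response stands under the secondary endpoints, with the test "Chi-square test for group-wise comparison of response rates". A risk difference and an NNT "will be calculated"; no covariate is named for either.

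The inclusion criteria in 6.2 set no minimum pain score.

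**The concern.** Response means baseline minus final score of at least 3, so the starting score enters the definition. A participant who starts at 1 or 2 cannot respond whatever the gel does. One who starts at 3 must reach 0, and one who starts at 8 need only reach 5. Eligible conditions run from sprains to Kellgren-Lawrence grade III osteoarthritis, so a wide spread of starting scores is plausible.

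Section 7.4.2 treats baseline as worth adjusting for when it analyses the score, then leaves it out for the response built from that score. At stake is the width of the interval around the risk difference. So is the extent to which the observed risk difference and NNT reflect a chance gap in starting pain between arms of 54 to 60.

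**Working it through.** **Inputs from the protocol.** 54 evaluable and 60 recruited per arm (6.7); pain-score SD 1.81 (6.7, which does not say whether this is the SD of the final score or of change); threshold 3 (5.1); alpha 0.05 in general (7.4.2) and 0.05/3 = 0.0167 for pairwise comparisons (6.7).

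**Assumptions, because the protocol is silent.** Response rates, and the correlation r between baseline BPI and response.

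**Step 1: the plan's own figure.** There is none for the response: no expected rate, margin or power. The 54 per group in 6.7 is for the pain score and is used here only as a head count. (It does not follow from its printed inputs: 2.39 + 0.84 = 3.23, not 4.059, and (3.23 × 1.81)² = 34.2. That is a separate matter.)

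**Step 2: interval width.** The 95% half-width of the unadjusted risk difference is 1.96 × √(2p(1−p)/n).

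- p = 0.5, n = 60: 0.179
- p = 0.5, n = 54: 0.189
- p = 0.7, n = 60: 0.164

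Adjustment multiplies the variance by about 1 − r², and so the half-width by √(1 − r²). From 0.179 this gives 0.171 at r = 0.3, 0.164 at r = 0.4 and 0.155 at r = 0.5. The interval is narrower by about 1 to 2.5 percentage points on each side.

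**Step 3: power to detect a difference.** For 50% vs 70% at 60 per arm and alpha 0.05:

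- Unadjusted: (0.2 − 1.96 × √(2 × 0.6 × 0.4/60)) / √((0.25 + 0.21)/60) = (0.2 − 0.1753)/0.0876 = 0.28, so power is 61%.
- Adjusted, r = 0.4: effective n = 60/(1 − 0.16) = 71.4. Then (0.2 − 0.1607)/0.0803 = 0.49, so power is 69%.

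Gain in percentage points for the same rates:

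| Alpha | Unadjusted power | r = 0.1 | 0.2 | 0.3 | 0.4 | 0.5 |
|---|---|---|---|---|---|---|
| 0.05 | 61% | 0.4 | 1.8 | 4.2 | 7.7 | 12.6 |
| 0.0167 | 44% | 0.5 | 1.9 | 4.4 | 8.3 | 14.0 |

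Other assumed pairs (40% vs 60%, 60% vs 80%, 50% vs 75%), at 54 or 60 per arm, give gains of 10 to 15 points at r = 0.5 and about 0.5 at r = 0.1.

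**Step 4: simulation of the risk difference.** Chi-square was compared with logistic regression on baseline plus a standardised risk difference: 60 per arm, alpha 0.05, 2,000 trials per setting, response about 48-50% vs 68-71%. Variance reduction is 1 − (adjusted SE/raw SE)².

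| r | SE raw | SE adjusted | Variance reduction | Power gain (points) |
|---|---|---|---|---|
| 0.08 | 0.0863 | 0.0856 | 1.6% | 1.0 |
| 0.21 | 0.0863 | 0.0839 | 5.5% | 2.2 |
| 0.32 | 0.0865 | 0.0813 | 11.7% | 4.6 |
| 0.41 | 0.0870 | 0.0783 | 19.0% | 8.5 |
| 0.49 | 0.0874 | 0.0747 | 26.9% | 13.3 |

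A second simulation started from scores: integer BPI, baseline mean 5.5 and SD 1.8, control final mean 2.8, final SD 1.81, a true 1-point shift, 54 per arm, alpha 0.05. Power was 46% vs 56%, 54% vs 63% and 73% vs 78% at baseline-final correlations of 0.3, 0.5 and 0.7. The gain shrinks as that correlation rises, because the change then depends less on where the participant started. With no shift, both methods rejected in about 4-5% of trials.

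**Step 5: chance imbalance.** The between-arm gap in mean baseline has SD √(2/n): 0.192 baseline SDs at n = 54 and 0.183 at n = 60 (95% range about ±0.38 and ±0.36). With the assumed SD of 1.8 and n = 54, one SD of the gap is 0.192 × 1.8 = 0.35 points and two SDs are 0.69. In the score-based simulation each 1-point gap moved the crude risk difference by 0.09 to 0.14 and the standardised one by less than 0.02. A two-SD gap therefore moves the crude figure by 0.69 × 0.09 = 0.06 to 0.69 × 0.14 = 0.10, and the standardised one by less than 0.69 × 0.02 = 0.014.

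**The case against.** **The response is only secondary.** Section 7.4.2 makes the baseline-adjusted ANCOVA with TOST primary, and 6.7 sizes the trial on the pain score. A reader might infer from 5.1 and 7.9.1 that the primary analysis ignores baseline. The documents do not support that, because they disagree on which endpoint is primary. If 7.4.2 prevails, the point concerns a supportive analysis. It still holds there, since this is the only risk difference and NNT planned for the efficacy response.

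**Power to detect a difference is the wrong yardstick.** This stands. The objective in section 4 is equivalence, no margin is set for the response, and a logistic test of no difference would not supply one. Interval width is the better measure, and on that scale the gain is modest.

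**The size is assumed.** This also stands. A reader might take a fixed loss such as 5 to 10 points of power as established, but the protocol fixes neither response rates nor correlations. If change is unrelated to baseline, the gain is only about 1 to 2 points.

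**The chi-square test is valid.** True. A reader might infer bias or an inflated false-positive rate from chance imbalance. Under randomisation there is no bias on average, and the null simulations show the nominal error rate. What is lost is precision, and accuracy in the one trial that is run.

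**Estimation detail may sit in a SAP.** In part. The protocol does not say that the risk difference is crude. It does name the test, and that test takes no covariate.

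**Conclusion.** The point holds as a free improvement, not as an error that invalidates the analysis. The plan fixes an unadjusted test for a response that depends on the starting score, while the starting score is collected and already used elsewhere in 7.4.2.

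The variance of the risk difference would fall by roughly 10-25% if baseline correlates with response at about 0.3 to 0.5, and by very little below about 0.2. The corresponding power gain ranges from about 0 to 15 points. These figures rest on assumed baseline scores, final scores and response rates. The protection of the observed risk difference and NNT against chance imbalance likewise grows with the strength of that relation.

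Which endpoint is primary decides how much this matters, but not whether to do it.

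**What to change.** In 7.4.2, replace the chi-square test for the response with wording to this effect:

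> Response will be analysed by logistic regression on treatment group with baseline BPI as a continuous covariate. For each pairwise comparison the baseline-standardised (marginal) risk difference will be reported with its confidence interval, and the NNT will be derived from it. Crude response rates will be given descriptively.

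The covariate should be the baseline value of the same BPI measure that defines the response.

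Separately, reconcile 5.1 and 7.9.1 with 7.4.2 on whether the response or the mean score is primary.

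Cost: a short text change and a few lines of code, with no new data, visits or participants. It should be fixed before database lock, since adjustment added afterwards would look data-driven.

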7.7.2 Study period and process

The study period for each participant is defined as “the period from the day of consent to the end of study (the day on which final tests and observation are finished or the day of discontinuation of the study).

The participants considered as a complete visit after the 3rd visit examination on 6 ± 1 days visit.

[figure not shown]
- 1st visit consider as Day 0
- 2nd visit is on Day 3 ± 1 days
- 3rd visit is on Day 6 ± 1 days

The study's flow in Day 0 :

- 1) The registration officers will receive participants who register at the Eminence clinic and ask about symptoms related to the participant's visit. If the Participant complains of pain, the patient will be asked to fill out a registration form.
- 2) The Principal Investigator or Sub Investigator will ask some questions (anamnesis) about the symptoms and explain about a clinical study that is conducted in the clinic. The PI or Sub-I will ask the Participant's willingness to join the research and explain regarding informed consent. If the Participant agrees, an informed consent will be signed.
- 3) The participants are asked to complete the Individual Assesment of Pain.
 - a. Form 2 : Pemeriksaan Inventerisasi Rasa Nyeri Singkat
- 4) The examination was carried out by conducting anamnesis, physical examination to confirmation the musculoskeletal pain, range of motion and muscle test and confirmation related to the inclusion and exclusion criteria. If needed a radiologic examination will be conducted.
- 5) In the examination, the PI or Sub-I should complete some Forms :
 - a. Form 3 : Pemeriksaan Awal Rasa Nyeri
 - b. Form 4 : Pemeriksaan Indikator Rasa Nyeri Non Verbal
 - c. Form 5 : Pemeriksaan Rentang Gerak
 - d. Form 6 : Pemeriksaan Kekuatan Otot
- 6) The PI or Sub-I will provide a diagnosis and therapy appropriate to the diagnosis.

- 7) Randomization of participants is carried out helped by Study Coordinator. The administration of therapeutic drugs according to the randomization list by a physiotherapist. The physiotherapist will provide information related to how to apply topical drugs to participants and provide the first dose of the investigational product in the therapy room.
 - a. Form 7: Pemberian aplikasi obat topikal by Physiotherapist
 - b. Form 8: Sensasi Termal by Participant
- 8) Each participant will get physical therapy program referred to standard protocol and diagnosis

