7.9.2 Secondary Endpoint

The assessment of secondary endpoints will be assessed through :

- Form 3 : Pemeriksaan nyeri awal pasien
- Form 4 : Pemeriksaan indikator rasa nyeri non verbal
- Form 5 : Pemeriksaan rentang gerak
- Form 6 : Pemeriksaan kekuatan otot

By Principal Investigator or Sub Investigator on 1st Visit, 2nd Visit and 3rd Visit.

- Form 8 : thermal sensation, thermal comfort, and thermal acceptance and time of thermal sensation.

By Participant on 1st Visit, 2nd Visit and 3rd Visit.

- Adverse events symptoms, concomitant medication, rescue medication that will be described in the Diary Participant.

By Participant on Day 0 until study is completed.

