7.10 STATISTICAL ANALYSIS

7.4.1 Analysis Sets

In the efficacy analysis, the **Per Protocol Set (PPS)** will be used as the primary analysis set, while the **Full Analysis Set (FAS)** will serve as the secondary analysis set. For safety analysis, the **Safety Analysis Set** will be used. The definitions are as follows:

- **Per Protocol Set (PPS):**
The PPS includes participants who do not have any major protocol violations (such as not meeting inclusion/exclusion criteria or poor compliance), and who have completed the required assessments of the primary endpoint as specified in the protocol.
- **Full Analysis Set (FAS):**
The FAS includes all participants who received at least one dose of the study drug and had at least one post-baseline assessment for efficacy endpoints. This set reflects the intention-to-treat principle.
- **Safety Analysis Set:**
The Safety Analysis Set includes all participants who received at least one dose of the study drug and had at least one post-baseline safety assessment. All safety data, including adverse events and rescue medication use, will be analyzed in this set.

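### Rescue use is compared as mean doses per participant in a set that keeps early leavers, so unequal dropout can distort the comparison; a rate per day observed should be compared, with raw doses and days observed beside it

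*Protocol*

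**What the plan says.** Protocol section 7.4.2, under Safety Analysis, has two lines on rescue medication. The test is "Poisson regression or negative binomial regression if data are overdispersed". The measure is "Summarized as a mean number of doses used per participant and compared between groups". The protocol gives no rate per day and no person-time denominator for rescue use.

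Section 7.4.1 fixes the population: "All safety data, including adverse events and rescue medication use, will be analyzed in this set". Entry to that set needs little follow-up: "The Safety Analysis Set includes all participants who received at least one dose of the study drug and had at least one post-baseline safety assessment".

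Follow-up is not the same for everyone. Section 7.7.2 ends a participant's study period on "the day on which final tests and observation are finished or the day of discontinuation of the study". Section 7.9.2 has rescue use recorded in the diary "By Participant on Day 0 until study is completed". For completers, "3rd visit is on Day 6 ± 1 days", so their span is 5 to 7 days. The missing-data rule at the end of section 7.4.2 concerns the primary endpoint only.

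**The concern.** A count of doses depends on how long the person was observed. Averaging counts over participants, some observed for two or three days and others for six, mixes need for rescue with length of follow-up. If one arm loses more people early, its mean falls even when daily use is identical.

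Leaving may also be related to pain. Section 7.8.1 lists worsening of the target disease as a reason to discontinue, and section 6.4 covers participants who need an unacceptable concomitant medication. Unequal dropout between arms is therefore possible for reasons tied to the outcome.

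All arms may take rescue paracetamol (section 6.10), and the primary ANCOVA and TOST analysis in section 7.4.2 does not adjust for it. The rescue comparison helps a reader judge whether similar pain scores came with similar extra analgesia, so its denominator should be sound.

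**Working it through.** The protocol gives no expected figure for rescue use, so there is none to reproduce.

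**Inputs from the protocol.** 60 participants per arm, 180 in total, and 10% dropout (section 6.7), which is 18 people. Follow-up is 6 days with a window of ±1 day, and visit 2 is on day 3 ±1 (section 7.7.2).

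**Assumptions.** Leavers stop on day L = 1, 2 or 3. The true daily rate is constant and equal in the two arms, and the same for leavers and completers.

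**Formula.** With leaver fractions dA and dB, the ratio of raw mean doses is

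[1 − dA(1 − L/6)] / [1 − dB(1 − L/6)].

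The correct answer is 1.00.

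- 15% vs 5%, day 2: (1 − 0.15 × 4/6) / (1 − 0.05 × 4/6) = 0.900/0.967 = 0.93.
- 15% vs 5%, day 3: 0.925/0.975 = 0.95. Day 1: 0.875/0.958 = 0.91.
- 20% vs 0%: day 3 0.90, day 2 0.87, day 1 0.83.
- 10% vs 10%: 1.00 for any leaving day.

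With 10% in the third arm, both 15%/5% (9 + 3 + 6) and 20%/0% (12 + 0 + 6) total the 18 planned dropouts.

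**Effect on the test.** I used simulated Poisson and negative binomial regressions with 60 per arm and 800 runs per scenario. Leavers stopped on day 3. Assumed rates were 0.5 or 1 dose per day, and assumed dispersion was 0 or 1, treated as known. False-positive rates at the 5% level were:

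| Leavers | No offset | log(days) offset |
|---|---|---|
| 10% vs 10% | 4 to 6% | 4 to 6% |
| 15% vs 5% | 4 to 9% | about 5 to 6% |
| 20% vs 0% | 9 to 25% | 4 to 7% |

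The upper ends without offset are pure Poisson at 1 dose per day; overdispersed counts give the lower values. With the offset, the estimated ratio lay between 0.98 and 1.03.

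**Visit window.** A second simulation spread completers evenly over 5 to 7 days in both arms, with leavers at day 2. The raw ratios were 0.929 (15% vs 5%) and 0.866 (20% vs 0%), almost the same as with a fixed 6 days. The window adds noise, not a difference between arms.

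**If leavers are heavier users.** Let completers use r doses per day and day-2 leavers h × r. A leaver records 2hr and a completer 6r, so a leaver lowers the mean only if h < 3. At h = 3 the raw ratio is 1.00 whatever the dropout. Full follow-up at those rates, with 15% vs 5% leavers, would give (0.85 × 6 + 0.15 × 18) / (0.95 × 6 + 0.05 × 18) = 7.8/6.6 = 1.18. The per-day ratio is (6/5.4)/(6/5.8) = 1.07, using mean days of 0.85 × 6 + 0.15 × 2 = 5.4 and 0.95 × 6 + 0.05 × 2 = 5.8. An offset moves the answer towards full follow-up but does not remove informative leaving.

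**If use is front-loaded.** Assume the daily rate halves every 2 days, so the first 3 days carry 73.9% of six-day use. At 20% vs 0% with day-3 leavers, the raw ratio is 1 − 0.20 × 0.261 = 0.95. Mean days fall to 1 − 0.20 × 0.5 = 0.90 of full, so the per-day ratio is 0.948/0.90 = 1.05. The error has about the same size in the other direction.

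**The case against.** The best defence is that the test line and the summary line are separate. An exposure offset is routine in Poisson and negative binomial models, the protocol does not exclude one, and a separate analysis plan may specify it. That stands as far as the model goes: a reader might infer that the regression ignores days observed, but the text does not say so, and silence on an offset would not be a finding. It does not rescue the summary line, which positively names doses per participant as the measure compared.

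Second, someone who leaves because the gel fails may be a heavy rescue user. Section 6.10 sets a maximum of 3 doses per 24 hours unless the investigator advises otherwise, so two days at that maximum is 6 doses. A six-day completer at the assumed 0.5 to 1 dose per day records 3 to 6. That leaver equals or raises the arm's mean. A reader might infer that early withdrawal always makes an arm look better on rescue use; the documents do not support that.

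Third, two further readings go too far. The 5-versus-7-day span among completers might be taken as a bias of up to 40%, but it compares individuals, and nothing suggests the window differs by arm. Rescue use might be called the main check on equivalence, but no section says so: it sits under Safety Analysis. The primary efficacy set is the Per Protocol Set, which requires completed primary-endpoint assessments, so early leavers are largely outside the primary comparison.

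Fourth, a per-day rate is not a clean replacement when use is front-loaded. That stands and shapes the fix.

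**Conclusion.** The point holds in a limited form. The measure the protocol names has no time denominator, it is applied to a set that keeps partial follow-up, and it is biased when daily rates are equal and dropout is not. At 15% versus 5% leavers the bias is about 5 to 7% (ratio 0.95 to 0.93, leaving on day 3 or 2). It is nil with balanced dropout and becomes material only with strongly unequal dropout, such as 20% versus 0%. At the planned 10% overall it is modest.

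These sizes rest on assumed leaving days and a constant daily rate shared by leavers and completers; the false-positive rates also rest on assumed dose rates and dispersion. The direction is conditional on how much leavers used. This is a small improvement to a supporting analysis and does not undermine the primary equivalence test.

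**What to change.** In section 7.4.2, keep the stated Poisson or negative binomial model and add log(days of diary observation) as an offset. Make the rate per participant-day the compared measure, with rate ratios and confidence intervals. Report raw doses per participant and days observed by arm in the same table, so that a reader can see whether the two measures disagree and whether dropout was uneven. Do not drop the raw count, given the overcorrection possible with front-loaded use. If a separate analysis plan exists, its wording should match.

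The cost is one model term and one extra table column. Diary entries, visit dates and the discontinuation day (sections 7.8.2, 7.9 and 7.9.2) are already collected, so no new data, visits or participants are needed. The change should be made before database lock.
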